5.2 OUTCOME VARIABLES

5.2.1 PRIMARY OUTCOME VARIABLES

The primary outcome variables will be **adherence to acute and preventive migraine management strategies**. All primary outcome variables will be assessed through an electronic headache diary.

Adherence to Acute Migraine Management Strategies.

- a) **Treat Early:** When participants record headache activity, they will record type, timing, and current pain level for each acute medication dose taken. Treating early is operationalized as taking acute medication while the pain is mild.
- b) **Avoid Overuse:** Avoiding overuse is operationalized as taking fewer than 10 triptans and 15 non-specific pain medications (NSAIDs and acetaminophen) per month.

Adherence to Preventive Migraine Management Strategies:

- a) **Adherence to Preventive Behavioral Strategies:** Each participant will record information related to a single strategy: stress management, sleep management, or consistent eating. Participants will record either 1) whether they used a stress management strategy today (assessed each evening; Yes = adherent, No = non-adherent), or 2) when they got in and rose out of bed (consistent bedtime and rise-time; assessed each morning; Within 1 hour of median = Adherent, outside of 1 hr of median = Non-adherent).

Adherent), or 3) whether they ate at least three times that day (consistent eating, assessed each evening; Yes = Adherent, No = Non-adherent).

b) **Adherence to Preventive Medication:** If a participant is taking a preventive medication, they will record whether they took preventive medication each day. Taking preventive medication = Adherent, Not taking preventive medication = Not-adherent.

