6.1.3 Selection Of Instruments/Outcome Measures

All measures were selected using materials from the National Institutes of Neurologic Disorders and Stroke (NINDS) Common Data Elements (CDE) initiative. When possible, measures from the National Institutes of Health Patient Reported Outcome Measurement System (PROMIS) were selected. Primary outcomes were selected based on previous studies evaluating adherence to migraine management (5, 20, 27, 54, 55).

Surveys

All surveys to be used have been uploaded via the iRIS website.

Demographics

NINDS CDEs will be used to evaluate: Age; Gender; Ethnicity; Race; Sexual Orientation; Education Level; Marital/Partner Status; Employment Status; Household and Income; Overall Health; Medical History; Height and Weight.

Migraine Symptoms

American Migraine Study/American Migraine Prevalence and Prevention (AMS/AMPP) Diagnostic Module.

The AMS/AMPP Diagnostic Module (34, 56) is a survey based on the ICHD-2 criteria for migraine; migraine criteria remain unchanged in the updated ICHD-3b (1). The sensitivity and specificity for migraine are 100% and 82% respectively (56).

Allodynia Symptom Checklist (ACS). The ACS is a 12-item survey designed to assess cutaneous allodynia in people with migraine (57). Items assess frequency of allodynia symptoms, with response options ranging from none to $\geq 50\%$ of the time. Scale development identified here factors: thermal, mechanical static, and mechanical dynamic. Initial development indicated good psychometric qualities (57).

Medications

Preventive. Preventive medication name, dose, frequency and timing of administration, route of administration, and start date will be evaluated using the NINDS CDE for medications taken on a regular basis.

Acute. Acute medication name, dose, frequency, route of administration, and start date will be evaluated using the NINDS CDE for medications taken on an as-needed basis.

Literacy

Newest Vital Sign. The Newest Vital Sign is a 6-item survey that measures health literacy (58). Participants respond to open-ended questions about a nutrition label, which are coded as correct or incorrect. It has demonstrated reliability and validity in primary care and electronic health settings (58, 59).

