6.2 Assessments

6.2.1 Efficacy

The primary outcome variables will be **adherence to acute and preventive migraine management strategies**. All primary outcome variables will be assessed through the daily electronic headache diary, collected through the Status/Post app and captured by the REDCap system.

Adherence to Acute Migraine Management Strategies.

	When assessed	Question asked	Indication of adherence	Indication of non-adherence
Stress	each evening	whether they used a stress management strategy today	Yes	No
Sleep	each morning	when they got in and rose out of bed	Within one hour of median	Outside of one hour of median
Eating	each evening	whether they ate at least three times that day	Yes	No

Treat Early: When participants record headache activity, they will record type, timing, and current pain level for each acute medication dose taken. Treating early is operationalized as taking acute medication while the pain is mild.

Avoid Overuse: Avoiding overuse is operationalized as taking fewer than 10 triptans and 15 NSAIDS/acetaminophen per month.

Adherence to Preventive Migraine Management Strategies:

Adherence to Preventive Behavioral Strategies: Each participant will record information related to a single strategy: stress management, sleep management, or consistent eating. Participants will record either 1) whether they used a stress management strategy today (assessed each evening; Yes = adherent, No = non-adherent), or 2) when they got in and rose out of bed (consistent bedtime and rise-time; assessed each morning; Within 1 hour of median = Adherent, outside of 1 hr of median = Non-Adherent), or 3) whether they ate at least three times that day (consistent eating, assessed each evening; Yes = Adherent, No = Non-adherent).

Adherence to Preventive Medication: If a participant is taking a preventive medication, they will record whether they took preventive medication each day. Taking preventive medication = Adherent, Not taking preventive medication = Not-adherent.

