6.4 Statistical Method

6.4.1 Statistical Design

Basic descriptive statistics (e.g., means, standard deviations, frequencies) for variables of interest will be computed. Graphical approaches will be used to further explore the data where appropriate. The outcomes are either 1) repeated measures of binary adherence to each migraine management strategy [coded each day as 0 (did not adhere) or 1 (adhered)] or total number of non-adherence days for each migraine management strategy over the relevant time-frame. Longitudinal binary outcomes will be analyzed using randomized logistic models, and number of total non-adherence days will be examined using Poisson regression models. SAS 9.3 will be used in the analyses. All tests are two-sided using significance level 0.05.

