6.4.3 Planned Analyses

6.4.3.1 Primary Analyses

Primary Objective: Describe and analyze how individual differences and conditions influence adherence to preventive and acute migraine management strategies.

Phase 2 diary data will be utilized. Random effects logistic models will be used to examine the effects of individual differences (e.g., age and gender) and circumstances (headache days/last 7 days, variations in stress) on daily adherence to migraine management strategies during the initial three-month study period. The random effects logistic model is a kind of generalized linear mixed effects model which can take account of missing data due to drop outs. This type of analysis yields robust estimates even in situations when observations are missing both at random, and not at random. The total number of non-adherence days at the end of follow-up will also be obtained, and the effect of individual characteristics and conditions on the rate of non-adherence will be examined using Poisson regression model with log of length of follow-up as offset.

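### The preventive medication adherence rule counts days with no dose due as non-adherent, so a participant on a non-daily preventive who misses no dose would score far below 100%

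*Combined protocol and SAP*

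**What the plan says.** Section 5.2.1 makes adherence to preventive medication one component of the primary outcome. The recording unit is the calendar day: "If a participant is taking a preventive medication, they will record whether they took preventive medication each day". The scoring has two values: "Taking preventive medication = Adherent, Not taking preventive medication = Not-adherent". Section 6.2.1 (Efficacy) repeats the rule and adds no exception.

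Section 6.4.1 carries this into the analysis in two forms, a 0/1 code for each day and the "total number of non-adherence days for each migraine management strategy over the relevant time-frame". In section 6.4.3.1 the first form is modelled as "daily adherence to migraine management strategies during the initial three-month study period", and the second by a "Poisson regression model with log of length of follow-up as offset". Section 6.4.3.2 uses the same two models for the Phase 3 group comparison.

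The Phase 2 criteria in section 5.3.2 ask that the preventive and acute regimen be stable; they set no limit on dosing frequency. Section 6.1.3 says of the baseline record: "Preventive medication name, dose, frequency and timing of administration, route of administration, and start date will be evaluated". Table 6.1.3 places that record at Month 0. No section links it to the adherence score.

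**The concern.** Not taking a medication on a day when none is due is not non-adherence, but the rule as written has no other value to give that day. A participant on a non-daily schedule therefore accumulates non-adherent days simply by following the schedule. The Poisson offset does not correct this, because it is calendar follow-up and not the number of occasions on which a dose was due.

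At stake is the meaning of one primary outcome component. In the Phase 2 predictor models, a difference between participants in this score would partly be a difference in the type of regimen prescribed. In Phase 3, a non-daily user who already takes every dose cannot score higher by adhering better. Such users add noise to the comparison among preventive users and, if unevenly allocated, an imbalance.

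**Working it through.** There is no figure in the plan to reproduce. The detectable odds ratios in section 6.4.2 rest on a proportion of 0.37 for stress management and do not concern this outcome.

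**Inputs.** From the documents: the two-value rule (5.2.1, 6.2.1), daily coding and the count of non-adherent days (6.4.1), three months of Phase 2 diary data and the follow-up offset (6.4.3.1). Assumed: three months = 90 days; dosing intervals from every day to every 90 days, since the documents give none; every due dose taken and every day recorded.

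**Formula.** With D = 90 days and interval k, the number of doses due, n, is 90/k, rounded down or up according to where the first dose falls. Score under the rule = n/90. Non-adherent days = 90 − n.

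| Assumed interval | Doses due and taken | Score under the rule | Non-adherent days |
|---|---|---|---|
| Daily | 90 | 100% | 0 |
| Every 2 days | 45 | 50% | 45 |
| Weekly | 12–13 | 13.3–14.4% | 77–78 |
| Every 2 weeks | 6–7 | 6.7–7.8% | 83–84 |
| Every 28 days | 3–4 | 3.3–4.4% | 86–87 |
| Every 30 days | 3 | 3.3% | 87 |
| Every 84 days | 1–2 | 1.1–2.2% | 88–89 |
| Every 90 days | 1 | 1.1% | 89 |

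The correct score in every row is 100%, with no non-adherent days. In the Poisson model, the 30-day user has a rate of 87/90 = 0.97 non-adherent days per day of follow-up, where the correct value is 0.

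**Effect on a group mean.** This depends on the share f of preventive users on a non-daily product, which the documents do not give. As an illustration only, assume that daily users adhere on 80% of days and that all the others are fully adherent on a 30-day schedule. The measured mean is (1 − f) × 0.80 + f × (1/30), and the correct mean is (1 − f) × 0.80 + f:

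- f = 0: measured 80%, correct 80%
- f = 0.1: measured 72%, correct 82%
- f = 0.2: measured 65%, correct 84%
- f = 0.3: measured 57%, correct 86%

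**After the change.** If only occasions with a dose due are scored, a participant who takes every dose scores 100% at any interval, with no non-adherent occasions, provided each dose is matched to its due occasion. If the outcome is restricted to daily preventives, only the first row of the table remains.

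**The case against.** The strongest objection is that the affected group may be empty. No section mentions a weekly or monthly preventive, and the background (2.1) gives only beta-blockers and antiepileptics as common examples. This stands as a limit on size: with no non-daily users the bias is zero. It does not justify the rule, because the examples are not an eligibility restriction and nothing in the plan checks that every preventive is taken daily.

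Second, section 6.4.4 compares the randomised groups on the adherence outcomes from Phase 2 and adds adjusted analyses if a significant difference appears. A non-daily user's low score would already show in Phase 2, so this partly covers chance imbalance. The trigger is a significance test in a pilot with 30 per group, of whom only the preventive users count for this outcome. It also does nothing for the Phase 2 models.

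Third, the wording of the diary item is not shown (6.1.3, evening diary), and it might allow an as-prescribed or not-applicable answer. That is possible, but the written scoring has only two values.

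A reader might also infer more than the documents support:

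- That every non-daily user scores near 0%. That fits intervals of about two weeks or longer; every-other-day use gives 50%.
- That education or income will show a spurious association. No section links either to the type of preventive.
- That frequency is collected because regimens are known to differ. Section 6.1.3 gives no such reason, and frequency is recorded for acute drugs too.
- That entry to Phase 3 is distorted. Entry uses acute and preventive behavioural strategies, not preventive medication.

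**Conclusion.** The point holds in a conditional form. The rule as written is wrong for any preventive that is not taken daily, and no other section corrects it. For a participant who misses no dose over 90 days, the error runs from 50 percentage points (every other day) to about 96–97 points (every 28–30 days), and slightly more for longer intervals. These figures rest on assumed intervals and complete diaries.

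The overall bias cannot be sized, because the share of non-daily users is not given and may be zero. The effect is confined to one component of the primary outcome: the preventive medication analyses in the Phase 2 predictor models, and the Phase 3 comparison among preventive users. The documents do not support a claim that the trial's results are biased, only that the score is valid solely if all preventives are daily, which the plan neither requires nor verifies.

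**What to change.** Amend sections 5.2.1 and 6.2.1 so that the score uses the dosing frequency recorded at Month 0, in one of two ways:

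1. Score this outcome only for participants on daily preventives and set it to not applicable for the others. This is the simpler option and keeps the daily logistic model as planned.
2. Score only days or intervals in which a dose was due, and leave the rest out of both the logistic model and the count. For infrequent schedules, pre-specify how a due occasion is matched to a recorded dose, with a window, because frequency and start date do not fix due dates and a late dose would otherwise count as missed. Replace follow-up time with the number of scorable days or intervals as the Poisson offset for this outcome, in sections 6.4.3.1 and 6.4.3.2.

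Under either option, report how many participants use a non-daily preventive, overall and by randomised group.

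The cost is a wording change and a derivation step from data already planned, plus the matching rule under option 2. It changes scoring only, not anyone's treatment. The downside is that non-daily users contribute no data to this outcome under option 1 and little under option 2. Partial doses of a twice-daily drug are left out of this change: the documents show a single diary item on whether medication was taken, which may not support dose-level scoring.

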5.2.2 SECONDARY OUTCOME VARIABLES

Migraine Symptoms

- a) **Headache days** per 30 days as assessed by daily headache diary.
- b) **Average head pain severity** as assessed by daily headache diary.

Distress and Disability

- a) **Migraine-Related Disability** as assessed by the Migraine Disability Assessment (MIDAS) (36).
- b) **Migraine-Specific Quality of Life** as assessed by the Migraine-Specific Quality of Life Questionnaire (37).
- c) **Pain Interference** as assessed by the PROMIS-Pain Interference (38).
- d) **Depression symptoms** as assessed by the PROMIS-Depression Short Form (39, 40).
- e) **Anxious symptoms** as assessed by the PROMIS-Anxiety Short Form (39, 40).

Psychological Factors

- a) **Stress** as assessed by:
 - a. The Perceived Stress Scale (41).
 - b. The Daily Stress Inventory (42).
 - c. Daily ratings of perceived stress on a 0-10 numeric rating scale.
- b) **Sleep** as assessed by:
 - a. The PROMIS Sleep Disturbance (43).
 - b. A daily rating of sleep quality on a 5-point Likert-type scale ranging from “Very Poor” to “Very Good.”
 - c. A daily rating of sleep hours.
- c) **Headache Management Self-Efficacy** as assessed by the Headache Management Self-Efficacy (HMSE) scale (44)
- d) **Acute Medication Self-Efficacy** as assessed with the Acute Medication Self-Efficacy – Headache (AMSE-H) (45)
- e) **Study-Specific Self-Efficacy** as assessed by items based on the HMSE and AMSE-H, assessing self-efficacy for study-specific lifestyle and preventive medication adherence.
- f) **Outcome Expectancies** as assessed by items based on items used in other studies (46) to assess each preventive and acute migraine management strategy.
- g) **Catastrophizing** as assessed by the Pain Catastrophizing Scale (47, 48).
- h) **Locus of Control** as assessed by the Headache-Specific Locus of Control Scale (49).
- i) **Mindfulness** as assessed by the Five Factor Mindfulness Questionnaire (50).
- j) **Acceptance** as assessed by the Chronic Pain Acceptance Questionnaire (51).

Feasibility and Acceptability

- a) **Patient Satisfaction** as assessed by the Client Satisfaction Questionnaire (52).
- b) Perceived effectiveness of intervention as assessed by the **Program Evaluation** Survey (based on the program evaluation survey used in the Treatment of Severe Migraine Trial (33)).
- c) **Adverse Events** as assessed by the adverse events check-ins.
- d) **Adherence Rates** to the diary as assessed by proportion of entries completed.
- e) **Education Utilization** as assessed by rates of participant viewing each education module.

5.3 STUDY POPULATION

The study population will include adult patients enrolled in the Montefiore Medical System for at least one year who have been prescribed a triptan within one year. Potentially eligible patients will be identified using Clinical Looking Glass.

Patients who have been prescribed a triptan, ditran or gepant, or who have taken NSAIDs or acetaminophen in the past year will be identified using Clinical Looking Glass. The research coordinator will email appropriate patients (see “Introductory email to participants” attached). There is an opt-out option included in the email and only patients who have not opted out will be called. Those who meet eligibility criteria will be consented and enrolled into the study over the phone for Phase 1 (See “CDST stamped Oral Consent Form”, previously approved) and using the REDCap HIPAA-compliant data capture system for Phase 2 and 3. (Informed consent document previously approved).

Potential participants will also be recruited via internet resources such as Twitter, Facebook, and online postings (see “CDST Online Recruitment” and “CDST Online Recruitment - for Twitter” attached). The material directs potential participants to contact the study coordinator by email who will then pre-screen them.

Sampling will be stratified by gender [male = 30%; female = 70%; modeled after population migraine demographics (34)] to permit tests of the association of gender and adherence.

5.3.1 NUMBER OF PARTICIPANTS

There will be a total of 394 participants in this study. It will be necessary to screen 900 potential participants to meet this goal. This is a feasible goal: in the 8/2016-8/2017 period over 3,500 unique patients were prescribed a triptan across all providers in the Montefiore system.

5.3.2 ELIGIBILITY CRITERIA

Eligibility will be determined by a phone screen provided by a research assistant, supervised by the PI.

Inclusion/Exclusion Criteria Phase 1 (A & B):

Participants will be included if they 1) have an International Classification of Headache Disorders – 3 beta diagnosis of migraine, 2) self-report between 6 to 14 headache days per month, 3) are currently prescribed a triptan for acute migraine management, 4) are between the ages of 18 and 65, and 5) self-report at least one problem with adherence to preventive and acute migraine management strategies.

Exclusion criteria are 1) probable or confirmed medication overuse headache, 2) a plan to change, or changing preventive or acute migraine medication during study participation, and 3) are pregnant or are planning to become pregnant during study involvement (as triptans are Category C medications).

Inclusion/Exclusion Criteria Phase 2:

Participants will be included if they 1) have an International Classification of Headache Disorders – 3 beta diagnosis of migraine, 2) self-report and diary-confirmed 6 to 14 headache days per month, 3) are currently using one of the following treatments for acute migraine management: triptans, ditans, gepants, NSAIDs, or acetaminophen, 4) are stable on current preventive and acute treatment regimen for migraine, 5) are between the ages of 18 and 65, 6) reads English, 7) has capacity to consent, and 8) complete 80% of diary recordings in the first 30 days of monitoring.

Exclusion criteria are 1) probable or confirmed medication overuse headache, 2) a plan to change, or changing preventive or acute migraine medication during study participation, 3) are pregnant or are planning to become pregnant during study involvement (as triptans are Category C medications), 4) psychiatric illness or cognitive difficulties that would interfere with participation in the study, and 4) participated in Phase 1 of the Clinical Decision Support for Patient Migraine Management protocol.

Inclusion/Exclusion Criteria Phase 3:

Participants will be included if they 1) completed Phase 2 of the study, 2) completed at least 80% of diary recordings throughout Phase 2 of the study, and 3) demonstrated poor (<50%) adherence to at least one acute migraine management strategy and at least one preventive behavioral migraine management strategy during study Phase 2.

Exclusion criteria are 1) probable or confirmed medication overuse headache, 2) a plan to change, or changing preventive or acute migraine medication during study participation, 3) are pregnant or are planning to become pregnant during study involvement, 4) psychiatric illness or cognitive difficulties that would interfere with participation in the study.

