Participants will be included if they 1) completed Phase 2 of the study, 2) completed at least 80% of diary recordings throughout Phase 2 of the study, and 3) demonstrated poor (<50%) adherence to at least one acute migraine management strategy and at least one preventive behavioral migraine management strategy during study Phase 2.

Exclusion criteria are 1) probable or confirmed medication overuse headache, 2) a plan to change, or changing preventive or acute migraine medication during study participation, 3) are pregnant or are planning to become pregnant during study involvement, 4) psychiatric illness or cognitive difficulties that would interfere with participation in the study.

NUMBER OF PARTICIPANTS

There will be a total of 394 participants.

NUMBER OF STUDY SITES

[figure not shown]
The study will be conducted at:

[figure not shown]
The [name] (Headache & Adherence) Lab, [name].

The Montefiore Headache Clinic, [name].

STUDY FLOW CHART

Phase 1

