2. BACKGROUND

2.1 Background/Prevalence of Research Topic

Migraine is a chronic, painful condition with episodic attacks of head pain, nausea/vomiting, and sensitivity to light/sound (1). Migraine is common, affecting 1 in 7 Americans annually (2). Migraine is the most disabling neurological disease worldwide (3), and costs the U.S. healthcare system \$4.3 billion annually (4). Patient adherence to migraine treatment recommendations is problematic (5-7) and can lead to increased migraine symptoms, burden, and economic cost (5, 8-10). Some people with migraine use preventive migraine management to reduce migraine frequency, and virtually all people with migraine use acute migraine management to reduce the impact of migraine attacks (11-14). Adherence to preventive migraine management strategies involves consistent use of behavioral strategies (regulating stress, sleep, and diet) (15, 16) and sometimes medication (often beta-blockers or antiepileptics). For acute migraine management, triptans, ditans and gepants are the first-line strategy for moderate-severe migraines, and non-steroidal anti-inflammatories (NSAIDs) or acetaminophen are the first-line strategy for mild-moderate migraines (14, 17-19). Acute migraine medications are most effective if taken early during a migraine episode, when head pain is still mild (11, 20-22). Most acute migraine medication use should be limited to avoid medication overuse headache, a secondary headache caused by regular overuse of acute headache medication (Triptans \geq 10 days/month; NSAIDs and acetaminophen \geq 15 days/month). Thus, adherence to acute migraine management requires in-the-moment decision-making (11, 23). Little is known about who adheres to preventive and acute migraine management strategies (individual differences) and when patients adhere to these strategies (circumstances). Certain individual differences (age, gender, education, psychiatric comorbidity and patient beliefs) have been associated with retrospective reports of adherence and pharmacy refill in isolated studies (5, 8, 24-28). Changes in treatment conditions (time of day, weekly migraine frequency, variations in stress and sleep) may be implicated in adherence to acute migraine management strategies (8), but have not been empirically examined. Understanding individual variability in adherence is the foundation to targeting vulnerable populations with adherence interventions.

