6.3.7 Removal of Subjects

Phase 1: Participants will be removed if they choose to voluntarily withdraw.

Phase 2 and 3: Participants will be removed if they choose to voluntarily withdraw. Participants will be removed if they no longer meet any study inclusion/exclusion criteria (for example, if they do not have diary-

confirmed migraine, or if they initiate a new migraine medication during the study). Participants who withdraw for any reason will be given the option of continuing to use the app if they choose.

All participants will be provided with a synopsis of their diary data to be used in their routine clinical care following the study.

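### The overuse-headache exclusion and removal rule overlap with the primary outcome Avoid Overuse, so loss after randomisation is outcome-related, and ditan- or gepant-only users have no limit to be scored against

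*Combined protocol and SAP*

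**What the plan says.** Section 5.2.1 makes Avoid Overuse a primary outcome: "Avoiding overuse is operationalized as taking fewer than 10 triptans and 15 non-specific pain medications (NSAIDs and acetaminophen) per month". Section 6.2.1 (Efficacy) repeats the two limits. Neither section gives one for ditans or gepants, although Phase 2 admits users of "triptans, ditans, gepants, NSAIDs, or acetaminophen" (5.3.2).

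Section 2.1 describes medication overuse headache as "a secondary headache caused by regular overuse of acute headache medication" and attaches 10 days a month for triptans and 15 for NSAIDs and acetaminophen. Section 5.3.2 excludes "probable or confirmed medication overuse headache" in Phase 2 and again in Phase 3. Section 6.3.7 adds, for both phases: "Participants will be removed if they no longer meet any study inclusion/exclusion criteria". Its examples are missing diary confirmation of migraine and starting a new medication. Overuse headache is not named, but the rule covers every criterion.

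For those who leave early after randomisation, section 6.3.6 asks for the satisfaction and program surveys and an adverse-event assessment. Section 6.3.7 lets people who withdraw keep the app. No section says whether their later diary data are collected for analysis. Section 6.4.5 states that the random effects logistic model stays robust under missingness both at random and not at random.

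Phase 3 entry requires, among other things, that the participant "demonstrated poor (<50%) adherence to at least one acute migraine management strategy". Avoid Overuse is one of the two acute strategies.

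**The concern.** The people most likely to fail Avoid Overuse month after month are also the people most likely to be judged to have the excluded condition. Before randomisation this narrows the range of the outcome, which also affects the Phase 2 analysis of who adheres. After randomisation it is more serious, because participants can leave the comparison for a reason tied to the outcome. The CDST Medication module teaches appropriate use of acute medication (section 6.1) and the control app does not. If the module works, fewer CDST participants should reach the point of removal, and the control arm would lose more of its failures.

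Separately, a participant who uses only a ditan or a gepant has no limit to exceed. Such participants either score adherent whatever they take or have no defined score. In the first case they carry no information about the intervention and dilute the arm difference.

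**Working it through.** **1. The plan's own figure.** The documents give no rate, effect or power for Avoid Overuse. The nearest figure is in section 6.4.2: 80% power for an odds ratio of 1.28 with 30 per group. The base proportion stated there is 0.37, for stress management, with correlations up to 0.6. A Wald check uses SE = 1/√(60 × 0.25 × m_eff × 0.37 × 0.63) and detectable OR = exp[(1.96 + 0.84) × SE], with 90 days, or 79 after the stated dropout.

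- Exchangeable, 0.6: m_eff = 90/(1 + 89 × 0.6) = 1.65, SE = 0.416, OR 3.21.
- AR(1), 0.6: OR 1.37 to 1.40.
- AR(1), 0.4: OR 1.27 to 1.29.
- Independent days: OR 1.17 to 1.18.

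A correlation structure that the text permits can give 1.28, so I do not call it wrong. It concerns a daily outcome at 0.37 and does not carry over to a monthly overuse score.

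**2. Is failing the outcome the same as having the condition?** No. The numbers match but the units differ: the outcome counts medications in a month, while section 2.1 counts days and describes a headache caused by regular overuse.

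- Two triptans on each of 5 days: 2 × 5 = 10 triptans, a failure on 5 medication days.
- With 6 to 14 headache days, 10 to 14 triptan days are possible.
- NSAIDs once per headache day give at most 14, below 15. Two on each of 8 days give 16, a failure.

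**3. How often might it be failed?** Assumptions: headache days uniform on 6 to 14, 50% to 90% of them treated, a second dose on 0% to 50% of treated days. By simulation, 2% to 81% of months have 10 or more triptan doses, 2% to 43% have 10 or more triptan days, and 0% to 42% have 10 or more doses on fewer than 10 days. That range is too wide to place the outcome at or away from a ceiling.

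**4. Removal after randomisation, direction only.** Assume 6 of 30 controls (20%) fail in all 3 months and the other 24 never fail. Assume the CDST turns the same 6 into people who fail one month of 3 and are not removed. Ignore other dropout.

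- CDST: 6/90 = 6.7%.
- Control, none removed: 18/90 = 20.0%. Difference 13.3 points; odds ratio (18/72)/(6/84) = 3.50.
- Control, 3 of the 6 removed after month 1: (3 + 9)/84 = 14.3%. Difference 7.6 points; odds ratio (12/72)/(6/84) = 2.33.
- Control, all 6 removed after month 1: 6/78 = 7.7%. Difference 1.0 point; odds ratio (6/72)/(6/84) = 1.17.

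The pull toward no difference arises because removal follows persistence. If the same fraction r of failed months were lost in both arms, each arm's odds would be multiplied by (1 − r). The odds ratio would then be unchanged, although fewer failures would be left to estimate it.

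**5. Users without a limit.** If a share g always scores adherent and the rest fail at monthly rate f, adherence = 1 − (1 − g)f, and the arm difference = (1 − g)(f_control − f_CDST). With f = 20% against 10%, the difference is 10 points at g = 0, 9 at g = 10% and 6 at g = 40%. The share is not given; 10% to 40% is an assumption.

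**6. Phase 3 entry through Avoid Overuse.** Adherence below 50% over three months needs at least 2 failed months. With independent months the probability is 3f²(1 − f) + f³: 0.1% at f = 2%, 2.8% at 10%, 10% at 20%, 35% at 40%. The route exists, but those who enter by it are the most exposed to the Phase 3 exclusion.

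**The case against.** A reader might infer that Avoid Overuse can hardly be failed, that it sits at its ceiling, or that its failures disappear from the data. The documents do not support this. Steps 2 and 3 show that a month can be failed without reaching the day counts in section 2.1, and the Phase 3 entry rule itself treats Avoid Overuse as something participants can fail. Removal reaches people judged to have overuse headache, not everyone over the monthly count, and the plan describes no procedure for detecting that condition during follow-up. Any power figure would rest on an assumed rate.

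A second defence is that a failed month is already in the diary before removal. If removal depended only on recorded data, and those data stayed in the analysis, a correctly specified mixed model would largely cope. This is fair, but the plan says neither. The judgement may draw on information outside the recorded outcome, and such a model gives no general protection when data are missing not at random, whatever section 6.4.5 says. The planned Poisson model with a follow-up offset gives less weight to people removed early.

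Third, Phase 3 is a pilot under a secondary objective, and Avoid Overuse is one of several adherence components. That limits the importance of the point but does not make the rule harmless.

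**Conclusion.** The point stands as an overlap between the exclusion, the removal rule and a primary outcome. Loss of persistent overusers after randomisation is related to the outcome, and the plan does not say how their data are handled. The expected bias is toward no difference, on the assumptions that the CDST reduces overuse and that removal becomes likelier as overuse persists. Its size is unknown, because the documents give no adherence rate and no removal rate; step 4 shows direction and is not a forecast. A ceiling is possible but not shown.

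The missing limit for ditans and gepants follows directly from the text. Its effect is proportional to a share that the documents do not report. This is worth correcting because the main repair is cheap, not because the outcome has been shown to fail.

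**What to change.** - **Sections 6.3.7 and 6.4.3.2:** after a criterion lapses in Phase 3, keep collecting diary data where the participant agrees. Analyse every randomised participant in the assigned group, whatever is decided about app use or treatment.
- **Section 6.4.5:** withdraw the claim of robustness to data missing not at random and do not rely on it.
- **Avoid Overuse analysis:** restrict it to participants using a drug class with a stated limit, identified from Phase 2 so that the subset is fixed before randomisation. Add a supportive analysis of acute-medication days per 30 days with the Phase 2 value as covariate.
- **Reconciliation by the sponsor:** bring the outcome definition, the exclusion and the Phase 3 entry rule into agreement. State whether the outcome counts medications or days, how a monthly score fits the daily coding in section 6.4.1, and whether entry through Avoid Overuse is intended. No clinical limit is proposed here.

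Cost: wording in the protocol and SAP, and some added follow-up of removed participants on the existing app. Their later data may include medication changes. The restricted analysis will use fewer than 60 participants if any use only ditans or gepants.
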